9.5 Interim Analyses

No formal interim analysis is planned for the study.

Analyses will begin with the primary DBL which is targeted to occur when all participants have completed the 24-week double-blind treatment period. The final DBL will occur when all participants have completed the 52-week treatment period and the Week 60 follow-up visit and/or the IPD/EOT visit. An additional analysis may be performed between the primary and final DBLs, to report data accumulating during the extension period if needed to support end of phase 2 decision making.

---

## LIST OF ABBREVIATIONS

Abbreviation or special term	Explanation
ADA	Anti-drug antibodies
AE	Adverse event
ALT	Alanine aminotransferase
ANCOVA	Analysis of covariance
AST	Aspartate aminotransferase
ATC	Anatomical therapeutic chemical
BLQ	Below the lower limit of quantification
BMI	Body mass index
CI	Confidence intervals
CU-Q2oL	Chronic Urticaria Quality of Life Questionnaire
CSP	Clinical study protocol
CSU	Chronic spontaneous urticaria
DAE	AE leading to discontinuation
DBL	Database lock
DLQI	Dermatology Life Quality Index
DRMI	Dropout reason-based multiple imputation
eCRF	Electronic case report form
EOT	End of treatment
ePRO	Electronic patient-reported outcome
EQ-5D-5L	European Quality of Life-5 Dimensions
FAS	Full analysis set
GGT	Gamma-GT
HSS7	Hives severity score over 7 days
LLOQ	Lower limit of quantification
ICF	Informed consent form
IP	Investigational product
IPD	IP discontinuation
ISS7	Itch severity score over 7 days
ITT	Intent-to treat
IVRS	Interactive voice response system
IWRS	Interactive web response system
MAR	Missing at random
MedDRA	Medical Dictionary for Regulatory Activities

Abbreviation or special term	Explanation
MI	Multiple imputation
MMRM	Mixed-effect model repeated measurements
MNAR	Missing not at random
MTP	Multiple testing procedure
CCI	[REDACTED]
PGI-S	Patient Global Impression of Severity
PK	Pharmacokinetics
PRO	Patient-reported outcome
PT	Preferred term
Q1	1st quartile
Q3	3rd quartile
Q4W	Every 4 weeks
Q8W	Every 8 weeks
RNA	Ribonucleic acid
SAP	Statistical analysis plan
SC	Subcutaneous
SD	Standard deviation
SI	System international
SOC	System organ class
TBL	Total bilirubin
UAS7	Urticaria Activity Score over 7 days
UCT	Urticaria control test
ULN	Upper limit of the normal
UPDD	Urticaria patient daily diary
VAS	Visual analogue scale
WOCF	Worst observation carried forward (post-baseline)

## AMENDMENT HISTORY

Category*: Change refers to	Date	Description of change	In line with the CSP?	Rationale
N/A				

\* Pre-specified categories are  
Primary or secondary endpoints; Statistical analysis method for the primary or secondary endpoints; Derivation of primary or secondary endpoints; Multiple Testing Procedure; Data presentations; Other

## 1 STUDY DETAILS

This statistical analysis plan (SAP) outlines the analyses to be generated for the global clinical study report (CSR). Additional analyses required for regional submissions will be prespecified in a separate analysis plan and will be submitted to the appropriate authorities.

### Study objectives

**Table 1 Study Objectives**

Primary Objective:	Estimand description / Endpoints
To determine the clinical efficacy of benralizumab compared to placebo in patients with CSU who are symptomatic despite the use of H 1 antihistamine treatment.	

Population: Full Analysis Set:

Endpoint: Change from baseline in ISS7 at Week 12

Intercurrent events: All data up to Week 12 will be included regardless of randomised treatment adherence or rescue medication received

Summary measure: difference in least squares mean change from baseline in ISS7 at Week 12 between benralizumab and placebo

Secondary Objectives:	Endpoint/variable:
To evaluate the effect of benralizumab compared to placebo on supportive measures of clinical efficacy in patients with CSU who are symptomatic despite the use of H 1 antihistamine treatment.	

Key secondary endpoint: change from baseline in UAS7 at Week 12a

Proportion of responders (UAS7 ≤ 6) at Week 12

Change from baseline in HSS7 at Week 12

Time to ≥ 5 point decrease (clinically relevant decrease) in ISS7

Proportion of participants with complete UAS7 response (UAS7 = 0) at Week 12

Measures of angioedema activity at Week 12 in participants with angioedema at baseline

Change from baseline in UCT at Week 12

To evaluate the effect of benralizumab on patient-reported health-related quality of life measures in patients with CSU who are symptomatic despite the use of H 1 antihistamine treatment.	

Change from baseline in CU-Q20L at Weeks 12 and 24

Change from baseline in DLQI at Weeks 12 and 24

To assess the PK and immunogenicity of benralizumab 30 mg and 60 mg in patients with CSU who are symptomatic despite the use of H 1 antihistamine treatment.	

Serum benralizumab concentration

ADA

**Table 1 Study Objectives**

To evaluate the longer-term effect of benralizumab compared to placebo at Week 24 on measures of clinical efficacy in patients with CSU who are symptomatic despite the use of H 1 antihistamine treatment.	
 
• Change from baseline in ISS7 at Week 24
 
• Change from baseline in UAS7 at Week 24
 
• Proportion of responders (UAS7 ≤ 6) at Week 24
 
• Change from baseline in HSS7 at Week 24
 
• Proportion of participants with complete UAS7 response (UAS7 = 0) at Week 24
 
• Measures of angioedema activity at Week 24 in participants with angioedema at baseline
 
• Change from baseline in UCT at Week 24
 

To evaluate the efficacy of administration of benralizumab Q8W versus Q4W up to Week 52 in patients with CSU who are symptomatic despite the use of H 1 antihistamine treatment.	Change from baseline in ISS7 at Week 52  Other supportive efficacy assessments at Week 52 in participants on a Q8W dosing regimen compared to those on a Q4W dosing regimen.
Safety Objective:	Endpoint/variable:
To assess the safety and tolerability of benralizumab in patients with CSU who are symptomatic despite the use of H 1 antihistamine treatment.	
Safety and tolerability will be evaluated in terms of AEs, vital signs, and clinical laboratory values.
 
Assessments related to AEs cover:
 
 
• Occurrence/frequency
 
• Relationship to IP as assessed by Investigator
 
• Intensity
 
• Seriousness
 
• Death
 
• AEs leading to discontinuation of IP
 
 
Vital signs parameters include systolic and diastolic blood pressure, and pulse, as well as respiration rate, body temperature, body weight, and height.
 
Assessments related to vital signs cover:
 
 
• Observed value
 
• Absolute and percent change from baseline values over time
 

Tertiary/exploratory	Endpoint/variable:
To evaluate the effect of benralizumab compared to placebo on healthcare resource utilisation due to CSU in patients with CSU who are symptomatic despite the use of H 1 antihistamine treatment.	Rate of CSU-related healthcare resource utilisation during the study
To evaluate the effect of benralizumab compared to placebo on overall severity of disease patients with CSU who are symptomatic despite the use of H 1 antihistamine treatment.	Change from baseline in PGI-S score at Week 12 and at Week 24
To evaluate the mechanism of action of benralizumab in patients with CSU refractory to H 1 antihistamine treatment.	CCI

**Table 1 Study Objectives**

CCI	
To evaluate the effect of benralizumab compared to placebo on general health status in patients with CSU refractory to H 1 antihistamine treatment.	Change from baseline in EQ-5D-5L domain and VAS scores

a The key secondary endpoint will use the same treatment policy strategy estimand as outlined for the primary endpoint.

ADA, anti-drug antibodies; AE, adverse event; CU-Q20L, Chronic Urticaria Quality of Life Questionnaire; CSU, chronic spontaneous urticaria; DLQI, Dermatology Life Quality Index; EQ-5D-5L, European Quality of Life-5 Dimensions; HSS7, hives severity score over 7 days; ISS7, itch severity score over 7 days; IP, investigational product; PGI-S, Patient Global Impression of Severity; PK, pharmacokinetics; Q4W, every 4 weeks; Q8W, every 8 weeks; RNA, ribonucleic acid; SAP, Statistical Analysis Plan; UAS7, Urticaria Activity Score over 7 days; UCT, Urticaria Control Test; VAS, visual analogue scale.

## 1.1 Study design

### 1.1.1 Overall Design

This is a Phase 2b, multinational, randomised, double-blind, parallel-group, 24-week placebo controlled study with a 28-week extension to evaluate the efficacy and safety of benralizumab in participants  $\geq$  18 years of age with CSU refractory to standard of care treatment, which may include second generation H1 antihistamines (at approved or up to 4 times approved doses) as monotherapy or in combination with leukotriene receptor antagonists and/or H2 blockers. The study is designed to evaluate 2 induction doses of benralizumab (60 mg and 30 mg) compared to placebo and to compare 2 maintenance dosing regimens (Q8W versus Q4W) in the 28-week extension period.

The study comprises the following consecutive periods:

- A 10-day to 4-week run-in period,
- A 24-week placebo-controlled, double-blind treatment period (comprising an initial 12-week ‘induction dose’ period followed by an additional 12-week dosing period),
- A 28-week blinded-to-dosing regimen extension period for maintenance treatment.

[figure not shown]
Following informed consent, all eligible participants will enter a run-in period of 10 days to 4 weeks during which inclusion/exclusion criteria will be assessed, medical history taken, and complete physical exam will be conducted. Potentially eligible participants will remain on a stable, locally-approved dose of their H1 antihistamine treatment throughout the run-in period. Participants will be provided with a handheld device to respond to Patient-Reported Outcome (PRO) questionnaires during the study.

Following the 10-day to 4-week run-in period, approximately 160 participants will be randomised at Visit 2 stratified by region, in a ratio of 3:3:3:3:4 (n=30:30:30:30:40), respectively, to one of the following 5 treatment sequences (see also Figure 1 and [Figure 2](#)):

- Benralizumab 60 mg Q4W until Week 12, 30 mg Q4W until Week 24, and 30 mg Q8W during the extension period until Week 52 (n = 30)
- Benralizumab 60 mg Q4W until Week 12, 30 mg Q4W until Week 24, and 30 mg Q4W during the extension period until Week 52 (n = 30)
- Benralizumab 30 mg Q4W until Week 12, 30 mg Q4W until Week 24, and 30 mg Q8W during the extension period until Week 52 (n = 30)
- Benralizumab 30 mg Q4W until Week 12, 30 mg Q4W until Week 24, and 30 mg Q4W during the extension period until Week 52 (n = 30)
- Placebo Q4W until Week 24, benralizumab 30 mg Q4W until Week 36, and 30 mg Q8W until Week 52 (n = 40).

Figure 1 presents an overview of IP administration for each randomised treatment group.

### Figure 1 Investigational Product Administration

[figure not shown]

a In the extension period, participants will receive benralizumab on a Q8W or Q4W dosing regimen, as predetermined at randomisation (Visit 2). Participants randomised to receive benralizumab Q8W in the extension period will also receive placebo at intervening study visits when they are not receiving benralizumab. Q4W, every 4 weeks; Q8W, every 8 weeks.

Up to Week 24 analyses at primary database lock (DBL), all analyses will evaluate the three initial dose treatment arms: benralizumab 60 mg (total n = 60), benralizumab 30 mg (total n = 60), and placebo (total n = 40). At final DBL after the extension period, analyses will be evaluating Q4W and Q8W dosing regimens, as well as the five randomised treatment groups.

For an overview of the study design, see [Figure 2](#). For further details see CSP Section 4.1.

**Figure 2 Study Design**

a To maintain the blind of the dosing regimen in the extension period, participants randomised to receive benralizumab Q8W will receive Q4W investigational product dosing including placebo administered Q8W, 4 weeks after their benralizumab administrations.

Participants and investigators will remain blinded to the treatment and regimen until the final DBL.

### 1.1.2 Investigational Product Dosing Regimen

Participants who meet entry criteria will be randomised 3:3:3:3:4 by the interactive voice/web response system (Interactive Voice Response System [IVRS]/Interactive Web Response System [IWRS]) to one of the 5 treatment sequences described in CSP Section 4.1.

Blinded investigational product (IP) (benralizumab or placebo) will be administered by subcutaneous (SC) injection at the investigational site Q4W for up to 48 Weeks. The final dose of benralizumab or placebo will be administered at Week 48 (Visit 14).

During the initial 12-week treatment period, IP will be administered as 2 SC injections at the same anatomical site with a distance of at least 3 cm between the 2 injections. After Week 12, IP will be administered as a single SC injection (CSP Section 6.1).

During the initial 12-week treatment period (Visits 2, 3 and 4) all participants will receive randomised initial dose of study medication Q4W, ie benralizumab 60 mg, benralizumab 30 mg, or placebo (Figure 1 and Figure 2).

After Week 12, all participants randomised to benralizumab (either 60 mg or 30 mg) will receive 30 mg benralizumab Q4W at Visits 5, 6 and 7 (ie, Weeks 12, 16 and 20; [Figure 1](#)). Participants receiving placebo will continue to receive placebo Q4W ([Figure 1](#)).

In the extension period (ie from Week 24) the dosing regimen of the original 5 randomised treatment sequences will apply [Figure 1](#) and [Figure 2](#)). Participants randomised to benralizumab (either 60 mg or 30 mg) will receive benralizumab 30 mg either Q4W or Q8W, at Visits 8 through 14. Participants initially randomised to placebo will receive benralizumab 30 mg Q4W at Weeks 24, 28, and 32 (ie, Visits 8, 9 and 10), followed by benralizumab 30 mg Q8W from Week 36 (ie, Visit 11 through 14, [Figure 1](#) and [Figure 2](#)). All participants on Q8W regimen will continue to receive SC injections containing placebo at their Q4W visit intervals ([Figure 1](#)), thus maintaining the blinded treatment regimen.

Please refer to the clinical study protocol (CSP) for more details.

## **1.2 Number of participants**

Approximately 240 participants will be enrolled/screened in order to achieve 160 eligible study participants randomly assigned to study intervention.

Up to Week 24, ie, prior to start of the extension period evaluating Q4W and Q8W dosing regimens, participants in both benralizumab 60 mg initial dose treatment arms will be considered as a single treatment group (total n=60), as will participants in both benralizumab 30 mg initial dose treatment arms (total n=60). Together with the 40 participants in the placebo treatment arm the above randomisation will provide a 3:3:2 ratio across the treatment group to assess the primary endpoint at Week 12.

This provides 90% power for statistical significance at the 2-sided 2.5% level within each induction dose comparison versus placebo if the assumed effect is a 4.7 point mean difference in change in ISS7 between benralizumab and placebo, assuming a SD of 6 for the change in ISS7 and a 10% dropout rate. These assumptions are in line with those for previous CSU trials ([Saini et al 2015](#)). The proposed sample size also provides a robust dataset to assess the key secondary endpoints, assess potential responders in sub-populations, and make a comparative assessment of the Q4W and Q8W dosing regimens in the maintenance period.

## **2 ANALYSIS SETS**

### **2.1 Definition of analysis sets**

Six analysis sets are defined below: all participant analysis set, full analysis set (FAS), safety analysis set, pharmacokinetic (PK) analysis set, extension period analysis set and placebo-to-benralizumab extension analysis set. Participants must have provided their informed consent.

If no signed informed consent is collected (major protocol deviation), then the participant will be excluded from all analysis sets defined below.

Note: "Enrolled" is defined as a participant's agreement to participate in a clinical study following completion of the informed consent process. Potential participants who are screened for the purpose of determining eligibility for the study but are not randomised to the study will be considered "screen failures", unless otherwise specified by the protocol.

### **2.1.1 All participants analysis set**

This analysis set comprises all participants who sign the informed consent form (ICF) for the study, and will be used for the reporting of disposition and screening failures.

### **2.1.2 Full analysis set**

The full analysis set will comprise all randomised participants who receive at least one dose of IP, irrespective of their protocol adherence and continued participation in the study.

Participants will be analysed according to their randomised treatment irrespective of whether or not they were prematurely discontinued, according to the intent-to treat (ITT) principle. Data for participants who withdraw consent to participate in the study will be included up to the date of permanent discontinuation.

All efficacy analyses will be performed using an ITT approach based on the FAS. For consistency, demographic and baseline characteristics will be presented using the FAS.

### **2.1.3 Safety analysis set**

The safety analysis set will comprise all participants who receive at least one dose of IP. Participants will be classified according to the treatment they actually received.

Erroneously-treated participants (eg, those randomised to treatment A but actually given treatment B) will be included in the group of the treatment they received. A participant who receives at least one dose of active IP will be classified as active and included in the active IP treatment group. A participant who receives both active dose regimens will be classified as the higher active dose regimen (ie, 60 mg). Any deviations from the randomised treatment will be listed and considered when interpreting the safety data.

All safety summaries and anti-drug antibodies (ADA) analyses will be based on this analysis set.

#### **2.1.4 Pharmacokinetic analysis set**

All participants who received benralizumab and from whom PK blood samples are assumed not to be affected by factors such as protocol violations (eg, received wrong dose) and who had at least one quantifiable serum PK observation post first dose.

All PK summaries will be based on this analysis set.

#### **2.1.5 Extension period analysis set**

All participants who start or carry on receiving at least 1 dose of benralizumab after the end of the Week 24 placebo-controlled period, and thus entering the extension period.

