4.1.2 Investigational Product Dosing Regimen

Participants who meet entry criteria will be randomised 3:3:3:3:4 by the interactive voice/web response system (Interactive Voice Response System [IVRS]/Interactive Web Response System [IWRs]) to one of the 5 treatment sequences described in Section [4.1](#).

[Figure 3](#) presents an overview of the IP that will be administered for each randomised treatment group.

Figure 3 Investigational Product Administration

^a In the extension period, participants will receive benralizumab on a Q8W or Q4W dosing regimen, as predetermined at randomisation (Visit 2). Participants randomised to receive benralizumab Q8W in the extension period will also receive placebo at intervening study visits when they are not receiving benralizumab.

Q4W, every 4 weeks; Q8W, every 8 weeks.

Dosing Regimen at Visits 2, 3, and 4 (Initial Double-blind 12-week Treatment Period)

All participants will receive randomised double-blind study medication Q4W at Visits 2, 3 and 4 (ie, Weeks 0, 4, and 8; [Figure 3](#)).

Dosing Regimen at Visits 5, 6, and 7

Participants randomised to receive either 60 mg or 30 mg benralizumab during the initial 12-week period will receive 30 mg benralizumab Q4W at Visits 5, 6 and 7 (ie, Weeks 12, 16 and 20; [Figure 3](#)).

Participants receiving placebo will continue to receive placebo ([Figure 3](#)).

Dosing Regimen at Visits 8 Through 14

At Week 24 (Visit 8), participants initially randomised to benralizumab 60 mg or benralizumab 30 mg will receive benralizumab 30 mg Q4W or Q8W according to their original randomisation at Week 2. Participants randomised to the Q8W regimen will receive placebo at Week 24 and benralizumab 30 mg at Week 28 ([Figure 3](#)).

At Weeks 24, 28, and 32 (ie, Visits 8, 9 and 10), participants initially randomised to placebo will receive benralizumab 30 mg Q4W. At Week 36 (ie, Visit 11), participants randomised initially to placebo will receive benralizumab 30 mg Q8W; these participants will receive placebo at Week 36 and benralizumab 30 mg at Week 40 (Visit 12) ([Figure 3](#)).

Participants transitioned to the benralizumab 30 mg Q8W dosing regimen will remain on the Q8W dosing regimen. Participants will continue to receive SC injections Q4W at the study site visits; thus, participants receiving benralizumab 30 mg Q8W will receive placebo at every other site visit ([Figure 3](#)).

The final dose of benralizumab or placebo will be administered at Week 48 (Visit 14).

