#### **4.2.8 Safety Analyses**

Safety analyses will be performed using the safety analysis set. Summaries for the first 24 weeks will be presented by the 3 induction dose treatment groups as noted in Section [4.2](#). Summaries for the overall study period will be presented by the 5 randomised treatment sequences, including totals for the Q4W and Q8W dose regimens.

A small number of key tables will also be presented for data in the extension period alone to explore the safety profile in the second 6 months of study treatment were a direct comparison of Q4W versus Q8W dosing can be made for patients previously receiving benralizumab, and to summarise time on benralizumab alone for patients previously receiving placebo.

Participants will be analysed according to the treatment they received. In general, the baseline value for statistical analysis is the last non-missing value prior to administration of the first dose of IP. Safety data will be presented using descriptive statistics. No safety data will be imputed.

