## 6 CHANGES OF ANALYSIS FROM PROTOCOL

Section 2.1.5 Extension period analysis set is added to identify all participants who enter into the extension period.

Sections 3.3.6 and 4.2.7.6 measures of angioedema activity, analyses added inclusion of all participants and subgroup of participants with history angioedema, in addition of those with angioedema at baseline. This will provide consistency with other studies and greater understanding of the disease and IP treatment.

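### The extension period analysis set is defined by a benralizumab dose, so a participant whose last injection is at Week 24 is outside it on Q8W but inside it on Q4W

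*SAP*

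**What the plan says.** - **The set.** SAP 2.1.5 admits "All participants who start or carry on receiving at least 1 dose of benralizumab after the end of the Week 24 placebo-controlled period" and treats meeting that condition as entering the extension.
- **Its purpose.** SAP section 6, listing changes from the protocol, says: "Section 2.1.5 Extension period analysis set is added to identify all participants who enter into the extension period".
- **When the extension starts.** SAP 1.1.2: "In the extension period (ie from Week 24) the dosing regimen of the original 5 randomised treatment sequences will apply". The Visit 8 injection is thus an extension dose.
- **What is injected at Week 24.** Protocol 4.1.2 opens with "At Week 24 (Visit 8), participants initially randomised to benralizumab 60 mg or benralizumab 30 mg will receive benralizumab 30 mg Q4W or Q8W", then qualifies this for the Q8W arms: "Participants randomised to the Q8W regimen will receive placebo at Week 24 and benralizumab 30 mg at Week 28". For the former-placebo arm, SAP 1.1.2 says: "Participants initially randomised to placebo will receive benralizumab 30 mg Q4W at Weeks 24, 28, and 32".
- **Where entrants matter.** SAP 4.2.8 says "A small number of key tables will also be presented for data in the extension period alone", with a direct Q4W versus Q8W comparison as one aim. SAP 3.4.1 starts the extension on-treatment AE window at the first dose in the extension, without requiring that dose to be benralizumab. It gives a separate end of the double-blind window to participants who do not enter the extension.
- **Populations named elsewhere.** Efficacy is on the FAS (SAP 2.1.2 and 4.1), safety on the safety analysis set (SAP 2.1.3, 4.1 and 4.2.8), and disposition on the all participants analysis set with by-visit counts in the FAS (SAP 4.2.1). No output is assigned by name to the extension period analysis set.

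**The concern.** An analysis set for the extension should admit participants by a rule that works the same way in every arm. This one depends on which syringe was active at Week 24, and the randomised regimen decides that. A Q8W participant must stay on IP four weeks longer than a Q4W participant to be counted as having entered, and Q4W versus Q8W is the contrast the extension was built to make.

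If a table uses this set as its denominator, Q8W participants who stop between Weeks 24 and 28 leave both numerator and denominator, together with any AE that made them stop. Their Q4W counterparts stay in. Separately, two parts of the SAP can give different answers on whether the same participant entered the extension, and the AE windows turn on that answer.

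**Working it through.** **Step 1: apply the rule arm by arm.** Take a participant whose last IP is the Week 24 (Visit 8) injection.

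| Sequence | Week 24 | Week 28 (not reached) | In set, SAP 2.1.5 | In set, any-IP rule |
|---|---|---|---|---|
| 60 mg then Q8W | placebo | benralizumab | no | yes |
| 30 mg then Q8W | placebo | benralizumab | no | yes |
| 60 mg then Q4W | benralizumab | benralizumab | yes | yes |
| 30 mg then Q4W | benralizumab | benralizumab | yes | yes |
| Placebo then benralizumab | benralizumab | benralizumab | yes | yes |

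The asymmetry would vanish only if the Week 24 injection were held to fall before the extension. SAP 1.1.2 rules that out by starting the extension at Week 24.

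**Step 2: compare with the AE windows in SAP 3.4.1.** Use nominal days after first dose. The last double-blind dose, at Week 20, is day 20 × 7 = 140. Week 24 is day 24 × 7 = 168.

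- If the Q8W participant in Step 1 has entered, the double-blind window ends on day 167. The extension window opens on day 168 and runs to day 168 + 30 = 198.
- If the participant has not entered (SAP 2.1.5 read literally), the double-blind window ends on day 140 + 30 = 170, two days after the Week 24 visit. AEs on days 171 to 198 then lie outside the double-blind window, in someone classed as a non-entrant, although 3.4.1 still gives that person a first extension dose on day 168.

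The whole-study on-treatment window is unaffected, because it runs to 30 days after the last dose of any IP, subject to the EOT visit.

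**Step 3: size.** The plan states no figure for this, so there is none to reproduce. Inputs: 60 participants per pooled maintenance regimen (SAP 4.1), and the 10% dropout used for sample size (Protocol 9.2, SAP 1.2). Applying that 10% to IP stopping after Week 24, and spreading it at constant hazard over T weeks, are assumptions.

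- Four-week risk: q = 1 − 0.9^(4/T)
- Expected Q8W participants excluded: 60 × q
- Chance of at least one exclusion: 1 − (1 − q)^60

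| T (weeks) | q | Expected of 60 | Chance of at least one |
|---|---|---|---|
| 52 | 0.0081 | 0.48 | 39% |
| 24 | 0.0174 | 1.04 | 65% |
| 12 | 0.0345 | 2.07 | 88% |

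The corresponding Q4W exclusion is 0 of 60 in every row. Using all 60 slightly overstates the count, since some will have stopped before Week 24. With 54 (60 × 0.9) at risk, the expected numbers are 0.44, 0.94 and 1.86. A four-week risk of 5% would give 60 × 0.05 = 3.

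**Step 4: after the change.** With entry defined by any IP dose at or after Visit 8, the last column of the first table applies and the differential exclusion is zero.

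**The case against.** The strongest reply is that nothing reported has to pass through this set. SAP 4.2.8 opens by placing safety analyses on the safety analysis set, and SAP 2.1.3 and 4.1 say the same. A Q8W participant with an AE between Weeks 24 and 28 is in that set. The Q4W versus Q8W efficacy comparisons at Week 52 are on the FAS. Disposition covers the extension on all participants. The extension tables are descriptive, and one or two people are involved. Section 6 also shows that all entrants were meant.

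Most of this stands. A reader might infer that the rule biases the trial's Q8W versus Q4W comparison, or makes Q8W look better tolerated and better retained by construction. The documents do not support that. Efficacy, disposition and full safety-set summaries do not use the set, and even in a table that did, tolerability would look better only if the one or two people removed had more AEs than those kept. Nor does it help to express the loss as a share of Q8W stopping between Weeks 24 and 48. Under almost any constant hazard that share is near 4/24 = 16.7%, so it says little about this trial.

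The reply leaves two gaps. The safety analysis set includes people who left before Week 24, and the SAP does not say how it is restricted to entrants for the extension-only tables. SAP 2.1.5 is the only set covering all five sequences that offers a rule, so its use there is possible but not stated. The second gap is that 3.4.1 relies on who enters the extension, whichever population a table uses. A clear intention in section 6 does not correct the definition in 2.1.5, which is what would be programmed.

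**Conclusion.** The defect in the definition is certain. SAP 2.1.5 conflicts with its stated purpose in section 6 and admits participants by a rule that differs between the regimens being compared. It also leaves entry ambiguous for the AE windows in 3.4.1.

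The consequence is small and conditional. It reaches only outputs that use this set, or its meaning of entry, to select extension participants; the extension-only tables in 4.2.8 are the likely candidates, but the SAP does not assign the set to them. About 0.5 to 2 of 60 Q8W participants would be affected, assuming 10% dropout at constant hazard over 52, 24 or 12 weeks. The documents give no rate for Weeks 24 to 28. This is a wording correction worth making, and it gives no reason to doubt the planned efficacy comparisons.

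**What to change.** Three edits to the SAP:

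1. In 2.1.5, replace the benralizumab condition with at least one dose of IP (benralizumab or placebo) at or after the Week 24 visit (Visit 8).
2. In 3.4.1, state that entering the extension period has this same meaning, so that each AE falls under one rule.
3. In 4.2.8, define the extension-only tables as participants in the safety analysis set who meet this rule, analysed by treatment received as that section already requires. Do not switch these tables to randomised sequence, which would conflict with 2.1.3 and 4.2.8.

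The placebo-to-benralizumab extension set can stay as it is, because that arm receives benralizumab at Week 24. The cost is a few phrases. No new data are needed, and neither dosing nor blinding changes.
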